3.5 Definitions

3.5.1 Treatment Failure

Treatment failure is defined as the first occurrence after randomization (Stage 2) or as the first occurrence after re-randomization (Stage 3) of any of the following events:

- Corticosteroid injections or treatment with a new or increased lupus medication, except the occasional use of corticosteroids for reasons not associated with SLE flare (see Section 7.1.2.2, *Prednisone (or equivalent)* for additional information); or
- BILAG flare, defined as any item marked new or worse that could support a BILAG A (severe flare) or 2 organs with items marked new or worse that could support a BILAG B (moderate flare), and if the participant's condition is deemed by the investigator to be "moderately worse" or "much worse" compared to the day of randomization, as assessed by the CGI-C; or
- Premature permanent discontinuation of study-assigned treatment for any reason.

For Stage 2, the reference values for the CGI-C should be the investigator's determination of the participant's condition at the Stage 2 Day 0 Randomization Visit. For Stage 3, the reference values for the CGI-C should be the investigator's determination of the participant's condition at the most recent assessment before the Stage 3 Re-randomization Visit.

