6.5 Premature Discontinuation of Investigational Agent

Study participants who discontinue investigational agent prematurely but are willing and able to remain in the study and undergo evaluation per protocol will be encouraged to do so.

Study therapy may be paused for up to 2 weeks for infections, gastrointestinal abnormalities, HTN, decreased eGFR, hematologic abnormalities and hepatic abnormalities as detailed in Section 6.4, *Toxicity Prevention and Management*.

Study therapy may be prematurely discontinued for any participant for any of the following reasons:

1. Participant decision.
2. Determination of unacceptable toxicity, including but not limited to:
 - a. Gastrointestinal abnormalities that do not resolve after study medications are withheld for up to 2 weeks as outlined in Section 6.4.5, *Gastrointestinal abnormalities*;
 - b. HTN that does not resolve after study medications are withheld for up to 2 weeks as outlined in Section 6.4.6, *Hypertension*;
 - c. Decreased eGFR that does not resolve after study medications are withheld for 2 weeks as outlined in Section 6.4.7, *Decreases in eGFR*;
 - d. Hematological Abnormalities that do not resolve after study medications are withheld for up to 2 weeks as outlined in Section 6.4.9, *Hematological Abnormalities*;
 - e. Hepatic Abnormalities that do not resolve after study medications are withheld for up to 2 weeks as outlined in Section 6.4.10, *Hepatic Abnormalities*;
 - f. Grade 4 Leukopenia (WBC < 1000/mm³, equivalent to 1.0 x10⁹/L); and
 - g. Grade 4 Neutropenia (Neutrophils < 500/mm³, equivalent to 0.5 x10⁹/L);
3. Treating physician determination of any condition that warrants withdrawal of study medication.
4. Any condition that in the opinion of the DAIT Medical Monitor warrants withdrawal of study medication.
5. The participant becomes pregnant.
6. The participant develops a malignancy (other than non-melanoma skin cancer).
7. Treatment failure, as defined in Section 3.5.1, *Clinical Endpoints* including corticosteroid injection(s) or treatment with a new or increased lupus medication.
8. Toxicity or Infection (see Section 6.4, *Toxicity Prevention and Management*):
 - a. If study medication is withheld for more than 14 sequential days due to suspected toxicity or infection.
 - b. Grade 4 infection.

7 Other Medications

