11.2 Participant Stopping Rules and Early Termination Criteria

Participants may be prematurely terminated from the study for the following reasons:

1. The participant elects to withdraw consent from all future study activities, including follow-up.
2. The participant dies.
3. The DAIT Medical Monitor no longer believes participation is in the best interest of the participant.
4. The investigator no longer believes participation is in the best interest of the participant.
5. The study is stopped.
6. The participant is “lost to follow-up.”

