13.4.2 Primary Analysis of Primary Endpoint

The primary endpoint is the cumulative incidence of treatment failure at or before the Stage 2 Week 24 visit. Time to treatment failure is defined as the interval from the day of Stage 2 randomization until the day of treatment failure (as defined in Section 3.2, Primary Endpoint). Participants who withdraw from the study early without evidence of treatment failure will be censored at day of the last assessment they were determined to be failure-free. The risk of treatment failure over the period of Stage 2 randomization through 24 weeks of follow-up will be presented graphically using Kaplan-Meier product limit estimates of the survival function in subgroups defined by treatment arm and by immunologically-homogenous subsets. The Kaplan-Meier estimates of event-free survival and confidence intervals using Greenwood's formula for standard error will be reported by subgroup at Stage 2 Week 24. The primary analysis will be a stratified two-sample test of the cumulative incidence of treatment failure at Stage 2 Week 24 using a 2-sided $\alpha=0.05$.

The ultimate goal of Stage 2 is to evaluate the potential effectiveness of MMF within the 7 previously-identified immunologically-homogeneous clusters for lupus. Regardless of the outcome of the stratified test for the pooled analysis, within-cluster landmark two-sample tests will be performed for comparisons of the cumulative incidence of treatment failure at Stage 2 Week 24 for each cluster. Due to the limited samples sizes anticipated in each immunologically-defined subgroup, no correction for multiple comparisons will be made, and p-values of < 0.10 will be considered notable findings but will be interpreted with caution given the high probability of a family-wise error with multiple comparisons under a strong null hypothesis of no treatment benefit.

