13.7 Sample Size Considerations

The goal of Stage 2 of the study is to evaluate the potential effectiveness of MMF within previously-identified immunologically-homogeneous clusters of lupus patients. To place these cluster comparisons in the context of a successful trial, target enrollment is based on power to show superiority of MMF over placebo in a pooled lupus population.

In previous studies using BOLD designs in lupus populations [22, 93, 94] where long-acting corticosteroids were administered during the treatment withdrawal stage, survival free-from-failure at 6 months in untreated or placebo-treated participants ranged from 5-20% [25]. These studies included participants with a range of disease activity, had differing rules on implementation of background steroids and different definitions for treatment failure. By limiting steroids and carefully adhering to entry criteria to recruit an appropriate population with active lupus disease activity, and by defining treatment failure to include individuals who receive rescue medications post-randomization or who withdraw from treatment prematurely, a placebo survival at 24 weeks of 15% or less should be achievable. In the MMF arm, a minimum clinically meaningful improvement would be 35% survival at 24 weeks.

A study design with 120 participants randomized 1:1 to placebo or MMF will have between 74% to \geq 95% power if placebo survival at Stage 2 Week 24 ranges from 15% to 10% and MMF survival at Stage 2 Week 24 ranges from 35% to 50% (2-sided, $\alpha=0.05$); power is \geq 80% when MMF survival at Stage 2 Week 24 is at least 37%. Power for a two-sample landmark analysis was computed for a Z-Test with unpooled variance using binomial enumeration.

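### Censoring of early study exits in Section 13.4.2 is not reconciled with Section 3.5.1, which makes any permanent end of assigned treatment a failure; the gap concerns exits before Week 24 with no flare, rescue or drug stop on record

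*Combined protocol and SAP*

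**What the plan says.** - **Endpoint.** Section 3.5.1 lists three routes to treatment failure. The third is "Premature permanent discontinuation of study-assigned treatment for any reason".
- **Planning.** Section 13.7 supports its placebo assumption (15% or fewer failure-free at Week 24) partly "by defining treatment failure to include individuals who receive rescue medications post-randomization or who withdraw from treatment prematurely".
- **Primary analysis.** Section 13.4.2 uses Kaplan-Meier estimates and a stratified two-sample test at Week 24. Its censoring rule is: "Participants who withdraw from the study early without evidence of treatment failure will be censored at day of the last assessment" at which they were found failure-free.
- **Stopping drug versus leaving the study.** Section 6.5 gives "Participant decision" as a reason for stopping drug. It encourages continued follow-up for "Study participants who discontinue investigational agent prematurely but are willing and able to remain in the study and undergo evaluation per protocol". Section 11.2 lists six reasons for leaving the study, among them "The participant elects to withdraw consent from all future study activities, including follow-up", "The participant dies", removal by the investigator or medical monitor, and loss to follow-up.
- **Clusters.** Section 13.4.2 adds: "The ultimate goal of Stage 2 is to evaluate the potential effectiveness of MMF within the 7 previously-identified immunologically-homogeneous clusters for lupus".

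No section says whether leaving the study is itself evidence of failure, or how each reason in 11.2 is to be coded.

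**The concern.** Someone who is taking study drug and leaves before Week 24 has permanently stopped assigned treatment. Section 3.5.1 read alone makes that an event. Section 13.4.2 read alone allows a censored observation if nothing else was recorded. Two analysts could code the same person differently and both cite the protocol.

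The two codings estimate different things. Counting the exit as an event estimates failure as 3.5.1 defines it. Censoring estimates the risk of the other failure criteria, with leavers assigned the later risk of those who stay, so that dropout is treated as non-informative. The choice affects the pooled test and the within-cluster tests. It also reaches the 48-week supportive analysis (13.4.3) and the Stage 3 repeat of the primary analysis (13.4.5). If it is settled only once exits by arm are visible, it becomes a data-driven choice.

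**Working it through.** **1. The plan's own figure.** Inputs from 13.7: 60 per arm, failure-free rates of 15% and 35%, two-sided 0.05, Z-test with unpooled variance, full binomial enumeration. Result: 73.8% (stated 74%). At 15% vs 37%: 80.7% (stated at least 80%). Both reproduce. The calculation gives every participant a known Week 24 outcome, which fits the failure rule and has no censoring term.

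**2. Who is affected.**

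| Situation before Week 24 | 3.5.1 | 13.4.2 | Conflict? |
|---|---|---|---|
| Flare or rescue recorded, then exit | Failure | Failure | No |
| Drug stop recorded, stays or leaves | Failure | Failure (evidence exists) | No |
| Consent withdrawn, or removed, with no documented drug stop | Failure, since treatment ends | Censored if exit is not evidence | Yes |
| Loss to follow-up, drug status unknown | Not named | Censored if exit is not evidence | Unsettled |
| Death | Not named; treatment ends | Censored if exit is not evidence | Unsettled |
| Study stopped | Not named | Ordinary administrative censoring | No practical issue |

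**3. Pooled effect.** The exit rates are assumptions. Let h be the weekly flare/rescue hazard, doubling at Week 12 (the shape in 13.7), and w a constant weekly exit hazard.

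- Failure-free under the failure rule: S(24) = exp(−36h − 24w), set to 0.15 (placebo) and 0.35 (MMF).
- Exit as first event by Week 24: w{[1 − e^(−12(h+w))]/(h+w) + e^(−12(h+w))[1 − e^(−12(2h+w))]/(2h+w)}, set to the assumed rate.
- Estimate when exits are censored: exp(−36h).

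For example, 5% exits on placebo give w = 0.0040 and h = 0.0500, so exp(−36 × 0.0500) = 16.5%. On MMF, w = 0.0031 and h = 0.0271, giving 37.7%.

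| Exits, placebo/MMF | Censored estimates | Difference | Change from 20.0 points |
|---|---|---|---|
| 5%/5% | 16.5% vs 37.7% | 21.2 | +1.2 |
| 10%/10% | 18.2% vs 40.7% | 22.4 | +2.4 |
| 4%/6% | 16.2% vs 38.3% | 22.1 | +2.1 |
| 5%/8% | 16.5% vs 39.4% | 22.9 | +2.9 |
| 5%/15% (extreme) | 16.5% vs 43.9% | 27.4 | +7.4 |
| 15%/5% (extreme) | 20.1% vs 37.7% | 17.6 | −2.4 |

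With these composite rates held fixed and equal exits, power is about 74% under either rule. If the flare/rescue rates are instead held at 15% and 35% and exits are added (simulation, 20,000 trials per scenario, censoring at the last four-weekly visit), power with exits as failures versus censored is:

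- 70.9% vs 72.7% at 5%/5%
- 68.6% vs 71.2% at 10%/10%
- 64.5% vs 69.6% at 15%/15%
- 55.0% vs 69.4% at 5%/15%
- 78.6% vs 72.5% at 15%/5%

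The documents do not say which quantity the 15% and 35% describe once exits occur.

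**4. One exit at Week 12.** Censoring passes that person's weight 1/n to those still at risk, of whom a fraction S(24)/S(12) remain failure-free. With the hazard doubling at Week 12, S(12) = S(24)^(1/3), so the shift is S(24)^(2/3)/n.

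- Pooled MMF: 0.35^(2/3)/60 = 0.497/60 = 0.8 point. Pooled placebo: 0.15^(2/3)/60 = 0.282/60 = 0.5 point.
- Cluster arm at 35%: 0.497/12 = 4.1 points to 0.497/5 = 9.9 points.
- Cluster arm at the 60% to 80% targeted in 13.7: 0.60^(2/3)/12 = 5.9 points to 0.80^(2/3)/5 = 17.2 points.
- Placebo cluster arm at 5% to 15%: 0.05^(2/3)/12 = 1.1 points to 0.15^(2/3)/5 = 5.6 points.

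The arm sizes of 5 to 12 come from 13.7 and assume that the seven clusters are evenly distributed.

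**The case against.** The strongest reply is that the censoring sentence already defers to 3.5.1. It covers only people with no evidence of failure, and 13.4.2 ties failure to Section 3.2, which points to 3.5.1. A known permanent drug stop is such evidence. An Early Termination Visit is requested (8.1.7) and capsules are counted at clinic visits (6.3), so many stops will be documented. That stands: it removes recorded drug stops from the concern and leaves mainly undocumented exits, loss to follow-up and death.

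It does not close the gap. If exit itself counts as evidence, the clause has almost no one to act on beyond study closure. Yet PP1 in 13.4.1.1 requires completion of Week 24 without failure, or failure by then, which implies that some participants do neither. The text does not say who they are.

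It is also fair that the large figures need unequal exits or very small arms. In an arm of five, any one outcome carries 20 points. Section 13.4.2 already urges caution on the cluster tests, and Stage 3 is supportive.

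A reader might infer that censoring inflates type I error. The calculations do not support that. With equal composite rates and 5%/15% exits, simulated results favouring MMF reach 7.0% to 10.2% under censoring, against 2.6% to 3.0% with exits as failures. But equal composites with more MMF exits imply a lower MMF flare/rescue hazard (0.0445 vs 0.0500 per week at 15%; 0.0229 vs 0.0271 at 35%). With equal flare/rescue hazards and the same exits, censoring gives 2.6%. The rules test different hypotheses.

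**Conclusion.** The concern holds in limited form. A stated primary-analysis rule and the endpoint definition are not reconciled for participants who exit on drug before Week 24 with nothing else recorded. This should be fixed, but it does not invalidate the design: the power figure is right, and no bias in the pooled comparison is shown.

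The pooled effect is about 1 to 2 points on the difference when exits are balanced at 5% to 10% per arm. It is larger only if exits differ by arm, and its direction depends on which arm loses more. The cluster estimates are more exposed: about 4 to 10 points per exit at 35% survival and 6 to 17 at 60% to 80%, in arms of 12 to 5.

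These sizes rest on assumed exit rates, a constant exit hazard independent of flare, a flare/rescue hazard that doubles at Week 12, unstratified tests in the simulations, and evenly distributed clusters.

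A reader might also infer that the protocol already makes death and loss to follow-up failures. It names neither in 3.5.1. Failure is the choice consistent with that section's wording on reasons, but for unknown drug status it remains an estimand decision that the documents leave open.

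**What to change.** In 13.4.2, state that 3.5.1 governs. Suggested text: *Any study exit before the Stage 2 Week 24 visit that ends assigned treatment (consent withdrawal, or removal by the investigator or medical monitor) is a treatment failure, dated at the last known dose or, if unknown, the last contact. Censoring is limited to administrative reasons, namely the study being stopped and the end of planned follow-up.*

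Then:

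- Map each of the six reasons in 11.2 to event or censoring. State explicitly how death and loss to follow-up with unknown drug status are classed in the primary analysis.
- Run the alternative classification, including the censored Kaplan-Meier analysis, as a named sensitivity analysis.
- Report exits by arm and reason, pooled and by cluster.
- Apply the same rule in 13.4.3 and 13.4.5.

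The cost is protocol and SAP wording, with no new data. Some exits unrelated to lupus or drug will count as failures, failure-free estimates will be slightly less favourable than under censoring, and a date must be assigned where the last dose is unknown.

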1.2.2 Rationale for Withdrawal of Background Medication

Since participants will be receiving a proven effective treatment for their immediate symptoms through steroid injections, this mitigates concerns that reduction of background treatments as early as the Screening Visit might precipitate a flare. Indeed, since all patients will be entered with active disease, the treatments being withdrawn will not be effective at that time point by definition. Safety is improved by allowing a washout of potentially interacting immune suppressants prior to starting the investigational treatment. Furthermore, simplification of background treatment early in the study will improve interpretability of both clinical and biomarker data, providing a valuable clarity for evaluation of the study treatment(s). In particular, the evaluation of MMF as a single agent will be facilitated by allowing it to exert its effects as a single agent from the start of administration.

Substitution of an ineffective treatment with a known, almost universally effective treatment (corticosteroid) is consistent with standard of care. The actual withdrawal of background treatment per se begins as a gradual decline in steroid levels over time. The earliest flares may start within a month, indicating that sufficient steroid dose was likely not given during the withdrawal phase. In the rare situations this does not ameliorate disease activity sufficiently for a participant to safely enter the trial, the participant will be taken off study, and they will be treated with whatever is appropriate at that time. Most flares in studies of this design occur after 2 or 3 months. This allows time to distinguish an effective treatment from placebo. As a flare becomes apparent, the participant becomes a non-responder in that part of the protocol and will also be immediately treated. Because of this, the trial design is in some ways easier to tolerate than some alternative protocols where participants who do not feel well must drop out or wait many weeks for treatment.

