3.1 Description of Study Design

This will be a multicenter, double blind, placebo-controlled Phase 2 trial of 120 participants with SLE who will enter with significant symptoms, but no organ-threatening disease. The study will be conducted in 3 stages.

3.1.1 Stage 1: Treatment Withdrawal:

During Stage 1, which may last up to 4 weeks, consenting participants will receive an IM injection of a long-acting corticosteroid, which may be repeated if needed to achieve amelioration of symptoms. A total of 3 corticosteroid injections may be given during Stage 1 with the first injection given as early as the Screening Visit after the mechanistic blood draw is completed and the last injection given as late as the Stage 2 Randomization Visit after the mechanistic blood draw is completed. Dose will be dependent on the available formulation.

In addition, participants will withdraw from all other treatments for lupus with the following exceptions: (i) PRN nonsteroidal anti-inflammatory treatments may be started or continued, (ii) PRN topicals may be continued, (iii) hydroxychloroquine, chloroquine, or quinacrine may be continued at any stable dose, and (iv) prednisone, if ≤ 10 mg/day, may be continued at stable doses but not started. Participants may screen if taking up to 20 mg/day prednisone (or equivalent) but both the participant and the investigator must be willing and able to taper to 10 mg/day (under cover of long-acting corticosteroids) by the Stage 2 Randomization Visit. Withdrawal of background lupus medications can start any time after the first corticosteroid injection is given but must be completed by the Stage 2 Randomization Visit.

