3.6 Stratification, Randomization, and Blinding

For Stage 2 randomization, participants will be stratified by screening gene expression signature:

- Group 1: high interferon and high inflammation
- Group 2: low inflammation and high B Cells (interferon can be high or low)
- Group 3: other profiles not included in groups 1 or 2
- Group 4: gene expression signature results unavailable (e.g. due to shipping or laboratory error)

For Stage 3 re-randomization, participants will be stratified by the Stage 2 treatment assignment: MMF vs Placebo MMF along with whether or not a long-acting corticosteroid injection was given at the time of Stage 2 treatment failure.

The randomization will be performed by the Division of Allergy, Immunology, and Transplantation (DAIT) Statistical and Clinical Coordinating Center (SCCC). Blinding will be maintained for all study participants and trial personnel throughout the study, except for the study site pharmacist. Treatment assignments will be centrally randomized and communicated to the unblinded study site pharmacist. The investigators, clinic personnel, and participants will not be informed regarding the intervention assignment until the study is unblinded. Laboratories performing assays for this protocol will be blinded to the identity and group assignment of biological materials to be studied.

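### The Stage 2 primary analysis makes no use of recorded Stage 1 steroid exposure (1 to 3 injections), a missed precision gain that is probably small

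*Combined protocol and SAP*

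**What the plan says.** Section 13.4.2 defines the primary test in one sentence: "The primary analysis will be a stratified two-sample test of the cumulative incidence of treatment failure at Stage 2 Week 24", at two-sided alpha 0.05. It names no steroid covariate. Section 3.6 gives the randomization factor: "For Stage 2 randomization, participants will be stratified by screening gene expression signature", in four groups. Steroid exposure is not among the factors.

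That exposure differs between participants. Section 7.1.1 requires at least one injection, and Section 3.1.1 sets the upper limit: "A total of 3 corticosteroid injections may be given during Stage 1". Repeats are given as needed, and the last may fall on the Randomization Visit. Section 7.1 has all concomitant medication entered on the eCRF.

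The plan treats the exposure as relevant to failure:
- Section 1.2.1 relies on the steroid effect waning to keep placebo response low.
- Section 1.2.2 says: "The earliest flares may start within a month, indicating that sufficient steroid dose was likely not given during the withdrawal phase".
- The log-rank simulation in Section 13.7 doubles the baseline hazard at Week 12 as the steroid attenuates.

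The nearest the analysis comes to using it is Section 13.4.3. Supportive Cox models there will explore covariates from study entry and from Stage 1. Injections are not named, and the models are left to the SAP.

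**The concern.** If participants with more or later steroid cover fail later, part of the outcome variation is known at baseline, and the primary test leaves it in the error term. With 60 per arm, a chance imbalance in injection count would also move the estimate, and no pre-specified adjustment would absorb it. An adjustment chosen after an imbalance is seen would carry less weight. The Cox models in 13.4.3 do not fill the gap, because a hazard ratio is not the Week 24 difference that the primary test addresses. Small gains have some value here, since planned power at the minimum clinically meaningful effect is 74%.

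**Working it through.** **Inputs from Section 13.7.** 120 randomized 1:1 (60 per arm) and two-sided alpha 0.05. On placebo, "a placebo survival at 24 weeks of 15% or less should be achievable". The minimum meaningful MMF survival is 35%. Power was computed for an unpooled Z-test by binomial enumeration.

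**The plan's own figures.** Exact enumeration at 15% versus 35% gives 73.8% (stated: 74%). At 15% versus 37% it gives 80.7% (stated: at least 80%). Both reproduce.

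**Assumptions, because the documents are silent.** Half the participants receive 1 injection and half receive 2-3. Placebo survival differs between these halves by 0, 10 or 20 points around a mean of 15%. On MMF, the gap around 35% is either the same as on placebo or wider (14 and 30 points).

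**Approximation.** Unadjusted SE = sqrt((0.15×0.85 + 0.35×0.65)/60) = sqrt(0.355/60) = 0.0769. Power = Φ(0.20/0.0769 − 1.96) = Φ(0.640) = 73.9%.

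A 50/50 covariate with gap g in an arm explains (g/2)² of that arm's variance. The share explained is therefore R² = [(g_placebo/2)² + (g_MMF/2)²]/0.355, and the SE is multiplied by sqrt(1 − R²).

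| Gap, placebo / MMF | R² | Power | Change |
|---|---|---|---|
| 0 / 0 | 0 | 73.9% | 0 |
| 10 / 10 | 0.0050/0.355 = 0.014 | Φ(0.659) = 74.5% | +0.6 |
| 10 / 14 | 0.0074/0.355 = 0.021 | Φ(0.668) = 74.8% | +0.9 |
| 20 / 20 | 0.0200/0.355 = 0.056 | Φ(0.717) = 76.3% | +2.4 |
| 20 / 30 | 0.0325/0.355 = 0.092 | Φ(0.768) = 77.9% | +4.0 |

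**Simulation (40,000 to 60,000 trials per scenario), like for like.**
- Gap 0: standardized risk difference 73.7% against 73.5% for the unpooled Z-test. Stratified CMH 72.1% against 71.9% unstratified.
- Gap 10 / 14: stratified CMH 73.2% against 71.9%.
- Gap 20 / 20: stratified CMH 75.1% against about 72.1%.
- Gap 20 / 30: standardized risk difference 77.9% against 73.8%. Stratified CMH 76.3% against 72.1%.

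Type I error of the standardized form was 5.4 to 5.6%, no worse than the 5.6 to 5.8% of the unpooled Z-test. These simulations leave out the signature strata and censoring.

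**Chance imbalance.** The SD of the between-arm difference in the share with 2-3 injections is sqrt(2×0.25/60) = 0.091. With a 20-point gap, a 1-SD imbalance moves the estimate by 0.091×20 = 1.8 points. That is 1.8/7.7 = 0.24 of the standard error.

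**Crossed strata.** Four signature groups × three injection levels × two arms make 24 cells, an average of 120/24 = 5 participants. Collapsing to 1 versus 2-3 leaves 16 cells and 120/16 = 7.5. Regression standardization avoids this thinning.

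**The case against.** The strongest reply is that the rationale concerns when failure happens, while the primary test asks whether it has happened by Week 24. Section 1.2.1 reports that all but 1 of 41 participants in the BOLD study lost their steroid response within 6 months, and the Section 1.2.2 sentence concerns flares within a month. Injections may shift timing more than Week 24 status. Repeats are also given by need, so a higher count means both more steroid and more resistant disease, and the two may cancel. Everyone must be at least moderately better before randomization (Section 4.2.2), which narrows the variation further. All of this stands, and it is why the gain is uncertain and probably small. It does not make adjustment harmful, since prognostic adjustment needs no causal direction.

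A second reply is that stratifying on a useless count costs power: 72.2% for a three-level CMH against 73.8% for the plan's Z-test. That compares two different tests. Within one test the cost is about zero.

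A reader might infer that Stage 3 shows an inconsistency, because it is stratified by Stage 2 arm "along with whether or not a long-acting corticosteroid injection was given at the time of Stage 2 treatment failure". The documents do not support that. It is a different injection, which is optional at Stage 2 failure, whereas everyone receives at least one in Stage 1. It is an analogy only.

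A reader might also infer that adjustment would lift power above 80%. A 26-point placebo gap does give 80.7%, but only with 2% versus 28% survival on placebo and 12% versus 58% on MMF. With equal gaps in both arms it gives 77.2%. Section 13.7 reports untreated or placebo survival of 5-20% across earlier studies with differing steroid rules, populations and failure definitions, a spread of 15 points from all causes. The 26-point gap exceeds that spread, and so does the 20-point gap, which is best read as an upper case.

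**Conclusion.** The point holds as a missed precision gain. The primary analysis and the Stage 2 strata leave out a recorded pre-treatment value that the plan's rationale ties to early failure, and the only other coverage is exploratory and unnamed. Under the assumed 50/50 split, power at 15% versus 35% changes by about 0, +1 and +3 to 4 points for placebo survival gaps of 0, 10 and 20 points. The 10-point case is the more plausible of the two non-zero ones. No single figure can be given, because the distribution of counts and their association with failure are not in the documents.

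It would be too strong to call the primary test biased or invalid. Randomization covers chance imbalance, and the standard error already reflects it.

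**What to change.** In Section 13.4.2, before unblinding, pre-specify the primary comparison as a regression-standardized Week 24 risk difference adjusted for randomization signature group and number of Stage 1 injections (1 versus 2-3). Do not add a crossed stratum. State how censored participants enter the estimate. Pre-specify time since last injection as a sensitivity analysis.

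Fix the covariate as of randomization. This requires reconciling the passages on Day 0 order. The synopsis Treatment Description and Section 4.2.2 place injections before randomization. Footnote I of Table 8.1 says only up to the day of randomization and before Stage 2 dosing. Section 3.5.1 counts a corticosteroid injection after randomization as treatment failure. As written, a Day 0 injection could be read as baseline exposure or as an event.

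The cost is analysis wording and a little programming, since the data are already collected. If the count proves non-prognostic, there is little or no gain and about no loss.
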